5.2 SAFETY PARAMETERS AND DEFINITIONS

Safety assessments will consist of monitoring and recording adverse events, including serious adverse events and adverse events of special interest, performing protocol-specified safety laboratory assessments, measuring protocol-specified vital signs, and conducting other protocol-specified tests that are deemed critical to the safety evaluation of the study.

Certain types of events require immediate reporting to the Sponsor, as outlined in Section 5.4.

5.2.1 Adverse Events

According to the ICH guideline for Good Clinical Practice, an adverse event is any untoward medical occurrence in a clinical investigation subject administered a pharmaceutical product, regardless of causal attribution. An adverse event can therefore be any of the following:

- Any unfavorable and unintended sign (including an abnormal laboratory finding), symptom, or disease temporally associated with the use of a medicinal product, whether or not considered related to the medicinal product

- Any new disease or exacerbation of an existing disease (a worsening in the character, frequency, or severity of a known condition) (see Section 5.3.5.9 and Section 5.3.5.10 for more information)
- Recurrence of an intermittent medical condition (e.g., headache) not present at baseline
- Any deterioration in a laboratory value or other clinical test (e.g., ECG, X-ray) that is associated with symptoms or leads to a change in study treatment or concomitant treatment or discontinuation from study drug
- Adverse events that are related to a protocol-mandated intervention, including those that occur prior to assignment of study treatment (e.g., screening invasive procedures such as biopsies)

5.2.2 Serious Adverse Events (Immediately Reportable to the Sponsor)

A serious adverse event is any adverse event that meets any of the following criteria:

- Is fatal (i.e., the adverse event actually causes or leads to death).
- Is life threatening (i.e., the adverse event, in the view of the Investigator, places the patient at immediate risk of death).

This does not include any adverse event that, had it occurred in a more severe form or was allowed to continue, might have caused death.

- Requires or prolongs inpatient hospitalization (see Section 5.3.5.11).
- Results in persistent or significant disability/incapacity (i.e., the adverse event results in substantial disruption of the patient's ability to conduct normal life functions).
- Is a congenital anomaly/birth defect in a neonate/infant born to a mother exposed to study drug.
- Is a significant medical event in the Investigator's judgment (e.g., may jeopardize the patient or may require medical/surgical intervention to prevent one of the outcomes listed above).

The terms "severe" and "serious" are not synonymous. Severity refers to the intensity of an adverse event (e.g., rated as mild, moderate, or severe; see Section 5.3.3); the event itself may be of relatively minor medical significance (such as severe headache without any further findings).

Severity and seriousness need to be independently assessed for each adverse event recorded on the eCRF.

Serious adverse events are required to be reported by the Investigator to the Sponsor immediately (i.e., no more than 24 hours after learning of the event; see Section 5.4.2 for reporting instructions).

5.2.3 Adverse Events of Special Interest (Immediately Reportable to the Sponsor)

Adverse events of special interest are required to be reported by the Investigator to the Sponsor immediately (i.e., no more than 24 hours after learning of the event; see Section 5.4.2 for reporting instructions). Adverse events of special interest for this study are as follows:

- Cases of potential drug-induced liver injury that include an elevated ALT or AST in combination with either an elevated bilirubin or clinical jaundice, as defined by Hy's Law (see Section 5.3.5.7).
- Suspected transmission of an infectious agent by the study drug, as defined below.

Any organism, virus, or infectious particle (e.g., prion protein transmitting transmissible spongiform encephalopathy), pathogenic or non-pathogenic, is considered an infectious agent. A transmission of an infectious agent may be suspected from clinical symptoms or laboratory findings that indicate an infection in a patient exposed to a medicinal product. This term applies only when a contamination of the study drug is suspected.

5.3 METHODS AND TIMING FOR CAPTURING AND ASSESSING SAFETY PARAMETERS

The Investigator is responsible for ensuring that all adverse events (see Section 5.2.1 for definition) are recorded on the Adverse Event eCRF and reported to the Sponsor in accordance with instructions provided in this section and in Section 5.4 to Section 5.6.

For each adverse event recorded on the Adverse Event eCRF, the Investigator will make an assessment of seriousness (see Section 5.2.2 for seriousness criteria), severity (see Section 5.3.3), and causality (see Section 5.3.4).

5.3.1 Adverse Event Reporting Period

Investigators will seek information on adverse events at each patient contact. All adverse events, whether reported by the patient or noted by study personnel, will be recorded in the patient's medical record and on the Adverse Event eCRF.

After informed consent has been obtained but prior to initiation of study drug, all adverse events caused by a protocol-mandated intervention (e.g., invasive procedures such as catheter insertion, biopsies, discontinuation of medications) should be reported. If the adverse event meets the criteria for serious adverse event, it should be reported immediately (see Section 5.4.2 for instructions for reporting serious adverse events).

After initiation of study drug, all adverse events will be reported until the follow-up visit or until the patient receives his or her first dose of study drug in the OLE study (Study BN40955), at which time reporting will occur per the new study requirements.

Instructions for reporting adverse events that occur after the adverse event reporting period are provided in Section 5.6.

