4.5.9 Magnetic Resonance Imaging

MRI images of the brain will be acquired (standard safety sequences, as well as structural MRI) at screening and at the follow-up visit (or at early termination visit, if applicable). Structural MRI is mandatory and must be performed at screening and at the follow-up visit (or at early termination visit, if applicable). As clinically indicated (and if patient gives specific consent), optional diffusion-weighted MRI may also be employed to examine structural brain connectivity and resting-state functional MRI may be employed to identify functional connectivity. All of the measures will be assessed at the whole-brain and regional levels.

MRI should be performed using a 3-Tesla (3T) magnet. The acquisition parameters of the sequence, structure, and length of each MRI session, as well as image-processing algorithms, will be outlined in a separate MRI manual. MRI scans will be managed by a central laboratory to monitor and ensure the integrity and quality of the acquired data. The screening MRI will be evaluated by the central laboratory to determine patient eligibility. During central review, the Sponsor and/or site staff will be notified of any unexpected findings requiring clinical follow up. Local neuroradiologists will be responsible for assessing MRI-related ongoing safety monitoring.

MRI should take place as early as possible within the screening window but may take place at any time during screening. The screening MRI scan should be performed at least 7 days prior to the IT catheter insertion to allow time for re-scanning if the quality of the initial MRI is inadequate. The screening MRI scan must pass central laboratory image quality control review and results must be available before the patient can be enrolled in the study.

The follow-up (or early termination, if applicable) MRI should take place within the 14-day window allowed for the follow-up visit (or early termination visit, if applicable) and prior to the lumbar puncture scheduled at the follow-up visit. If patient

who enrolled under protocol Version 3 cannot undergo and tolerate MRI scans, no MRI scans will be performed at the follow-up visit (or early termination visit, if applicable).

Anti-anxiety medication is prohibited during scheduled scans, as described in Section 4.4.2.

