5.1.1 Known Risks Associated with Lumbar Puncture

In the completed Phase I/IIa study, 46 patients were randomized to receive RO7234292 (n=34) or placebo (n=12). The most commonly reported adverse events across all treatment groups included procedural pain (54%) and post-lumbar puncture syndrome (37%). One patient who received placebo reported a serious adverse event of post-dural-puncture headache.

In the ongoing Phase II OLE Study BN40967 (15-month data cut), potential post-lumbar puncture adverse events (including procedural pain, post-lumbar puncture syndrome, post-procedural discomfort, *puncture site pain, headache, migraine, nausea, dyspepsia, backpain, malaise, and paraesthesia*) occurring within 72 hours of drug administration were summarized per cohort. For the Q4W cohort (n= 23), 35 events were reported in 14 (60.9%) patients; for the Q8W cohort (n=23), 36 events were reported in 12 (65.2%) patients.

Many of the complications associated with lumbar puncture can be avoided by the mandatory use of a 24G atraumatic needle with a stylet, adherence to procedural guidelines (see lumbar puncture manual and instructional video), and careful assessment of the patient, including neurologic examination with fundoscopy both prior and post the lumbar puncture procedure. Lumbar puncture should be avoided when contraindication is present.

CSF leakage is more likely with larger bore needles. To minimize this risk, a 24G atraumatic needle will be used. Training for use of the 24G atraumatic needle will be provided prior to initiation of lumbar puncture in the study, as will a review of extension tubing use and the need to gently aspirate CSF for timely collection. If headache with characteristics of low-pressure syndrome is present after the procedure and persists despite standard-of-care treatment, a blood patch should be considered. Formation of a subarachnoid epidermal cyst (i.e., when a skin plug is introduced into the arachnoid space) can be avoided by use of a needle with stylet, which is mandatory. Rarely, brain herniation can occur in the setting of lumbar puncture and increased intracranial pressure.

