5.4.2.2 Events That Occur after Study Drug Initiation

After initiation of study drug, serious adverse events and adverse events of special interest will be reported until the follow-up visit. Investigators should record all case details that can be gathered immediately (i.e., within 24 hours after learning of the event) on the Adverse Event eCRF and submit the report via the electronic data capture (EDC) system. A report will be generated and sent to Roche Safety Risk Management by the EDC system.

In the event that the EDC system is unavailable, the paper Clinical Trial Serious Adverse Event/Adverse Event of Special Interest Reporting Form provided to Investigators should be completed and submitted to the Sponsor or its designee immediately (i.e., no more than 24 hours after learning of the event), either by faxing or by scanning and emailing the form using the fax number or email address provided to Investigators. Once the EDC system is available, all information will need to be entered and submitted via the EDC system.

Instructions for reporting serious adverse events that occur after the follow-up visit are provided in Section [5.6](#).

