5.6 ADVERSE EVENTS THAT OCCUR AFTER THE ADVERSE EVENT REPORTING PERIOD

The Sponsor should be notified if the Investigator becomes aware of any serious adverse event that occurs after the end of the adverse event reporting period (defined as until the follow-up visit), if the event is believed to be related to prior study drug treatment. These events should be reported through use of the Adverse Event eCRF. However, if the EDC system is not available, the Investigator should report these events directly to the Sponsor or its designee, either by faxing or by scanning and emailing the paper Clinical Trial Serious Adverse Event/Adverse Event of Special Interest Reporting Form using the fax number or email address provided to Investigators.

5.7 EXPEDITED REPORTING TO HEALTH AUTHORITIES, INVESTIGATORS, INSTITUTIONAL REVIEW BOARDS, AND ETHICS COMMITTEES

The Sponsor will promptly evaluate all serious adverse events and adverse events of special interest against cumulative product experience to identify and expeditiously communicate possible new safety findings to Investigators, IRBs, ECs, and applicable health authorities based on applicable legislation.

To determine reporting requirements for single adverse event cases, the Sponsor will assess the expectedness of these events using the information in this protocol and the following reference document:

- RO7234292 Investigator's Brochure

The Sponsor will compare the severity of each event and the cumulative event frequency reported for the study with the severity and frequency reported in the applicable reference document.

Reporting requirements will also be based on the Investigator's assessment of causality and seriousness, with allowance for upgrading by the Sponsor as needed.

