- dd) After informed consent has been obtained but prior to initiation of study drug, any serious adverse events caused by a protocol-mandated intervention should be reported. After initiation of study drug, all adverse events will be reported until 6 months after the last dose of study drug. After this period, all deaths, regardless of cause, should be reported. In addition, the Sponsor should be notified if the Investigator becomes aware of any serious adverse event that is believed to be related to prior study drug treatment.
- ee) At the time of each study drug administration, an interval medical history should be obtained and any changes in medications, any major procedures or hospitalizations, and any physician visits for HD or general medical care should be recorded.

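### Adverse-event reporting ends at the visit where the last lumbar puncture is done, the stated end dates conflict, and later serious events caused by that puncture alone need not be reported

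*Protocol*

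**What the plan says.** **End of reporting.** Four places in the Protocol set it, and they do not agree.

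- Section 5.3.1, all adverse events: "After initiation of study drug, all adverse events will be reported until the follow-up visit". The sentence continues "or until the patient receives his or her first dose of study drug in the OLE study", after which the extension study's rules apply.
- Section 5.4.2.2: "serious adverse events and adverse events of special interest will be reported until the follow-up visit". There is no OLE alternative.
- Section 5.6 speaks of events "after the end of the adverse event reporting period (defined as until the follow-up visit"). Again there is no OLE alternative.
- Appendix 1, footnote dd: "After initiation of study drug, all adverse events will be reported until 6 months after the last dose of study drug". The follow-up visit itself may fall 14 days either side of the 6-month date.

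**Later events.** Section 5.6 asks for notification of a later serious event only "if the event is believed to be related to prior study drug treatment". Footnote dd repeats that condition and adds deaths from any cause.

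**The last puncture.** Section 4.5.9 places the follow-up MRI "prior to the lumbar puncture scheduled at the follow-up visit". Section 4.5.5 sets 20 mL of CSF for every needle puncture, with a 5 mL minimum if collection is difficult. Appendix 1 shows no contact after the follow-up visit.

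**Puncture harms.** Section 5.1.1 describes potential post-puncture events in the earlier OLE study, "occurring within 72 hours of drug administration were summarized per cohort". Section 5.1.1.1 gives headache after 10% of procedures in the Phase I/IIa study. Sections 5.1.1.2 and 5.1.1.3 name spinal hematoma and meningitis as puncture risks.

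**The concern.** The needle punctures on Days 29, 43, 71 and 127 are each followed by a scheduled visit at which adverse events are sought. The follow-up puncture is not. A complication that starts after the patient leaves has no scheduled route into the database unless the patient goes on to the OLE. If it is serious and attributed to the puncture rather than the drug, no rule requires the investigator to tell the sponsor.

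This matters because the plan intends to report procedural harm. Protocol Section 6.4 promises adverse-event incidence by relationship to study drug or procedure, and SAP Section 4.7.2 plans a separate summary and listing of procedure-related events. Before the first dose, Section 5.3.1 already requires events caused by protocol-mandated procedures to be reported. The rule after the last visit drops that category.

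**Working it through.** **1. The plan's own figures.** The 72-hour figures in Section 5.1.1 are the natural benchmark for the length of follow-up.

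- Q4W cohort: 14/23 = 60.9%, which agrees with the text.
- Q8W cohort: 12/23 = 52.2%, but the text gives 65.2%, which equals 15/23. Either the count or the percentage needs correcting. Neither figure is used below.

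**2. Collection time left after the follow-up puncture, patient not entering the OLE.**

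| Visit relative to 6 months | Sections 5.3.1, 5.4.2.2, 5.6 | Footnote dd |
|---|---|---|
| 14 days early | 0 days | 14 days |
| 3 days early | 0 days | 3 days (72 h just covered) |
| On the date | 0 days | 0 days |
| 14 days late | 0 days | 0 days; the puncture itself falls after the cutoff |

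Under the main text the gap is present whenever the visit occurs. Under footnote dd it closes only if the visit is early enough.

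**3. Can another section fill the gap?** Section 5.5.1 follows events already recorded, including serious ones related to study procedures, but does not collect new ones. Section 5.3.4 directs an event with a cause other than the drug to be judged unrelated. A complication of a puncture done about 6 months after the last dose would naturally be judged that way, so it fails the condition in Section 5.6. Only a death would still be reportable, under footnote dd.

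**4. Upper bound on missed headaches.** Inputs: 12 patients initially planned and at most 20 (SAP Section 2.5; Protocol Section 6.1); one follow-up puncture each; headache probability p = 0.10 per procedure (Section 5.1.1.1). Independence between procedures is assumed. Expected number = n × p; chance of at least one = 1 − (1 − p)^n.

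- n = 12: 12 × 0.10 = 1.2; 1 − 0.9^12 = 0.72.
- n = 20: 20 × 0.10 = 2.0; 1 − 0.9^20 = 0.88.
- With p assumed between 0.05 and 0.20, the expected number runs from 0.6 (n = 12) to 4.0 (n = 20), and the chance of at least one from 46% to 99%.

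**5. Effect on the planned tables.** SAP Section 4.7.2 counts a patient once per preferred term, so a missed headache changes that table only if the patient had none before. Over the five needle punctures (Days 29, 43, 71, 127 and follow-up):

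- All five collected: 1 − 0.9^5 = 0.410.
- First four only: 1 − 0.9^4 = 0.344.
- Difference 0.066, or 12 × 0.066 = 0.8 patients of 12 (1.3 of 20).

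The 1.2 to 2.0 in step 4 applies to the total event count, where SAP Section 4.7.2 counts repeats separately.

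**The case against.** A reader might infer that the whole round of follow-up punctures has no adverse-event follow-up, and that all the 72-hour harms described in Section 5.1.1 fall outside collection. The documents do not support that, for four reasons, all of which stand.

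- Appendix 1 marks adverse events at the follow-up visit, so events starting during the visit are captured. Procedural pain, one of the two commonest events in the Phase I/IIa study (54%), can start at the procedure itself.
- The OLE alternative in Section 5.3.1 can carry collection past the puncture for patients who enter the extension.
- Under footnote dd, an early visit leaves up to 14 days of collection.
- The 72 hours run from drug administration in a different study. No drug is given at the follow-up puncture and no onset distribution is reported, so the window is only a proxy.

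It can also be said that the secondary objective concerns the safety of two doses, so events after a drug-free puncture months later add little to it. That is fair for drug safety, but it does not answer the plan's stated intention to summarise procedure-related events. Finally, the most striking procedural harm in this study, lumbar abscess in 2 of 6 patients (Section 5.1.1.4), followed catheter placement and lies well inside the reporting period. It is not evidence about needle punctures.

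**Conclusion.** The point holds in a limited form. The four passages give conflicting end dates. For a patient outside the OLE, no rule or scheduled contact in the main text collects an event from the last puncture that starts after the visit. Under footnote dd the same is true when the visit is on time or late. A serious event attributed to the puncture alone is not reportable afterwards unless it is fatal.

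The headache figures of 1.2 in 12 patients and 2.0 in 20 are upper bounds. They assume that every patient reaches follow-up, none enters the OLE, the main-text end date applies and every headache starts after discharge. On the once-per-patient count the expected loss is at most about 0.8 of 12 patients. Section 5.1.1.1 describes these headaches as mild in the great majority, so the numerical bias is modest. The more important loss is a rare serious procedural event, whose frequency after needle puncture the documents do not give.

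**What to change.** 1. Reconcile Sections 5.3.1, 5.4.2.2, 5.6 and Appendix 1 footnote dd to a single end of reporting, set a short fixed interval after the puncture at the patient's last visit. Make the interval long enough to include at least the 72 hours of Section 5.1.1, used as a proxy, and close it with one telephone contact that asks about adverse events.
2. Apply the same rule to the early termination visit when that is the patient's last. CSF is sampled there too, and the main text does not state when reporting ends for such a patient; footnote dd would still cover it.
3. State the OLE alternative consistently in all four places or in none.
4. In Section 5.6 and footnote dd, extend later serious-event reporting to events believed related to study drug or to a study procedure.

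The cost is wording changes and one call per patient. Last contact moves by a few days. Treatment and visit procedures do not change.

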5.3.2 Eliciting Adverse Event Information

A consistent methodology of non-directive questioning should be adopted for eliciting adverse event information at all patient evaluation timepoints. Examples of non-directive questions include the following:

"How have you felt since your last clinic visit?"

"Have you had any new or changed health problems since you were last here?"

5.3.3 Assessment of Severity of Adverse Events

The adverse event severity grading scale indicated in [Table 2](#) will be used for assessing adverse event severity. Laboratory values determined as an adverse event should be graded as per [Appendix 7](#), which is based on National Cancer Institute Common Terminology Criteria for Adverse Events (v5.0).

Table 2 Adverse Event Severity Grading Scale

Severity	Description
Mild	Discomfort noticed, but no disruption of normal daily activity
Moderate	Discomfort sufficient to reduce or affect normal daily activity
Severe	Incapacitating with inability to work or to perform normal daily activity

Regardless of severity, some events may also meet seriousness criteria. Refer to the definition of a serious adverse event (see Section [5.2.2](#)).

